3.2 Statistical Hypothesis

The primary objective of the study is to evaluate the safety and tolerability of the column when used at blood-flow rates up to 450 mL/min. The safety and tolerability will be assessed at each column size and blood-flow rate to enable comparisons across those variables in each subject (intrasubject) and across all subjects. Because the primary objective of the study is safety and tolerability, the study is not designed to detect statistically significant differences and will be primarily descriptive.

3.3 Sample Size Justification

The sample size for this study was based on FDA Guidance for the Content for Premarket Notifications for Conventional and High Permeability Hemodialyzers (FDA 1998) which recommends that data be collected for a minimum of 12 subjects for a minimum of 36 treatments. In this study, approximately 15 subjects between 40 and 75 years of age with ESRD will be enrolled. Assuming a drop-out rate of 20% (unrelated to safety), enrollment will yield approximately 12 evaluable subjects. With regard to the most important risk of

IDH, a sample of 12 subjects will provide approximately 70% probability of detecting at least 1 IDH event in each week (i.e., for each column size and blood-flow rate combination). This estimate is based on the assumption that the rate of IDH in the general ESRD population, using the Nadir 90 definition, is 10%, based on a study in over 10,000

3.4 Randomization/Unblinding

US patients undergoing HD (Flythe 2015).

This is a non-randomized, open-label study.

3.5 Interim Analyses

Not applicable.

3.6 Study Assessment Time Points

The study consists of 23 protocol-specified visits, which will be assessed as nominal visits from an analysis perspective:

- 1) Visit 1 Screening: screening will be conducted at Days -35 to -7.
- 2) Visits 2 to 4, Run-In Period (Week -1): HD run-in period (no column) at 250 mL/min to determine Kt/V. Run-in will be conducted at Days -6 to -1.
- 3) Visits 5 to 22, Treatment Period (Week 1 to 6):
 - a. Visits 5 to 7 (Week 1): column S-15 at 250 mL/min. Visit 5 Day 1 is the day of the first use of the column. The escalation to the subsequent column-size and flow-rate combination will occur mid-week (e.g., on Wednesday for subjects on a Monday/Wednesday/Friday schedule and on Thursday for subjects on a Tuesday/Thursday/Saturday schedule).
 - b. Visits 8 to 10 (Week 2):

 column S-15 at up to 450 mL/min
 c. Visits 11 to 13 (Week 3):

 d. Visits 14 to 16 (Week 4):
 column S-25 at 250 mL/min
 column S-25 at up to 450 mL/min
 column S-35 at 250 mL/min
 column S-35 at up to 450 mL/min
 f. Visits 20 to 22 (Week 6):
- 4) Visit 23 EOS (Week 7): no column, HD at subject's standard rate. In the event of early withdrawal or discontinuation of a subject who has received at least 1 HD treatment with the column, the EOS procedures will be performed unless the subject has withdrawn consent.

3.7 Schedule of Events

Refer to Protocol Section 15.

3.8 Data Safety Monitoring Board (DSMB)

Safety oversight will be provided by the Sponsor's Program Physician or designee and the CRO's Medical Monitor(s) in concert with the site investigators. There will be no formal DSMB established. No DSMB analyses are planned in the SAP.

Statistical Analysis Plan AKST1210-101

Rev. A Page 11 of 28

4 Statistical Methodology

4.1 General Considerations

This section presents the statistical approaches that are anticipated for the analysis of the study data. These approaches may at times require modifications due to unanticipated features of the data. Deviations from analyses summarized in this document will be noted in the CSR.

All statistical analyses will be performed using SAS® Version 9.4 or higher, unless otherwise noted.

Data from this feasibility study will be analyzed mostly in a descriptive manner. Limited statistical comparison of outcomes across the various column-size and blood-flow-rate combinations will be performed. Details for any statistical tests are provided in the endpoint analysis sections (4.7, 4.8).

All safety endpoints will be summarized descriptively and tabulated as necessary, unless otherwise stated. Overall baseline and demographic data will be summarized using descriptive statistics.

For analysis of the primary and secondary endpoints, the following will be considered:

- For endpoints that are continuous in nature:
- Number of observations, mean, median, minimum and maximum, and standard deviation (SD) and change from baseline values (or percent change from baseline) will be presented as descriptive summary.
- For endpoints that are categorical in nature:
- Frequency counts and percentages will be presented as descriptive summaries.

Descriptive statistics will be utilized for trial conduct: screen failures, enrollment, withdrawal of consent, and study completion. Primary and secondary endpoints will be assessed at the beginning and end of each week of treatment for a particular column size and blood-flow rate combination. The effect of blood-flow rate will be assessed for a given column size as well as intrasubject and across-subject variability. The sample size was chosen based on clinical consideration of the study designed to test the safety and functionality of the column operated at higher blood-flow rates (up to 450 mL/min).

In general, all summary tables will be supported by a relevant subject data listing. The listings will include all data collected, and will be sorted by subject ID, and actual visit date, as applicable, unless otherwise noted. The listing will also include the column size and blood-flow rate combination as applicable.

Study day 1 is the first day of HD treatment with the day relative to the study day 1.

Statistical Analysis Plan AKST1210-101

Rev. A Page 12 of 28

Baseline is the first value after the start of HD with the column. For the assessments that do not take place during the treatment weeks (e.g., ECG, physical examination, etc.), the value from Screening will be the baseline. Baseline for lab values will be the last non-missing value prior to the start of HD with the column.

Change from baseline is the post-treatment value minus baseline value.

Subjects who de-escalate (i.e., do not proceed to the next column size and blood-flow rate combination) will only be included in analysis up to the point of de-escalation.

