17.1.2. De-escalation Rules

The purpose of the de-escalation rules is to ensure the safety of a subject who is experiencing IDH, anemia or other safety issues that may be related to the column size.

A subject should be de-escalated if during the 1-week treatment period they experience the number of IDH events described in the table above and/or have an Hgb level < 9 g/dL despite receiving optimized treatment with ESA.

De-escalation will only be applicable at V11 through V19 as shown in Figure 4 below. Subjects who do not tolerate treatment with the S-15 column at any time prior to V11 or after V19 will be discontinued (see Section 17.1.13. Discontinuation Rules).

Figure 4. De-escalation Schematic

Subjects will continue with the same visit schedule after de-escalation. At the visit following confirmation of de-escalation, treatment will resume with the previous column size at the high flow rate (up to 450 mL/min).

- ➤ If de-escalation occurs during V11 through V16, subjects will resume treatment at the next scheduled visit with the S-15 column at up to 450 mL/min and will continue with this column size/flow rate combination through EOT (V22).
- ➤ If de-escalation occurs during V17 through V19, subjects will resume treatment at the next scheduled visit with the S-25 column at up to 450 mL/min and will continue with this column size/flow rate combination through EOT (V22).

Table 4 below illustrates the visit schedule for subjects who de-escalate. *Note*: the only change compared to Section 15 is column size and flow rate.

Table 4. Schedule of Events for Subjects Who De-escalate

					,	Treatm	ent Peri	iod					EOS
Visit Number	V11	V12	V13	V14	V15	V16	V17	V18	V19	V20	V21	V22 (EOT)	V23
Study Week		Week 3			Week 4	ļ	,	Week 5			Week	6	Week 7
Study Day(s) (± 1)	Day 15	Day 17	Day 20	Day 22	Day 24	Day 27	Day 29	Day 31	Day 34	Day 36	Day 38	Day 41	Day 43
Procedure													
Physical examination													X
12-lead ECG													X
Targeted physical examination	X	X	X	X	X	X	X	X	X	X	X	X	
Weight	X	X	X	X	X	X	X	X	X	X	X	X	X
Vital signs ¹	X	X	X	X	X	X	X	X	X	X	X	X	X
Laboratory tests ²		X	X		X	X	X	X	X	X		X	X
Column size			S-	15			S-15	OR S-2	.5 (if de	e-escala	ated aft	er V16)	
Hemodialysis blood-flow rate (mL/min)						Up	to 450						
Assessment of fluid status	X	X	X	X	X	X	X	X	X	X	X	X	
Kt/V assessment		X			X		_	X			X	X	_
Adverse events and concomitant medications	X	X	X	X	X	X	X	X	X	X	X	X	X

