17.1.3. Discontinuation Rules

Subjects will be discontinued and complete the End of Study visit procedures if:

- Subject does not tolerate the S-15 column at either flow rate
- Subject does not tolerate the S-35 at the higher flow rate (up to 450 mL/min)
- Subject has already de-escalated and they experience the number of IDH events described in the Table 3 and/or have an Hgb level < 9 g/dL despite receiving optimized treatment with ESA
- At any time during the study at the investigator's discretion

As a reminder, all occurrences of IDH after the time of consent will be recorded as AEs.

^{2.} For additional information, see Section 15.3 Schedule of Laboratory Tests.

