4.7 Primary Analyses

Primary analyses will evaluate safety and tolerability of the column at blood-flow rates greater than 250 mL/min in subjects with ESRD undergoing HD. Except where indicated, primary endpoints will be summarized by each column size and blood-flow rate combination (S-15 250 mL/min, S-15 up to 450 mL/min, S-25 250 mL/min, S-25 up to 450 mL/min, S-35 up to 450 mL/min) and total using both Safety and Evaluable populations.

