4.7.1 Adverse Events

All treatment emergent adverse events (TEAEs) will be reported. A TEAE is defined as an AE that occurs on or after the date of the first column use.

A summary of all TEAEs, as reported in the EDC, by the number and percentages of subjects who experienced any of the following will be provided for the Safety population:

- Any TEAE, including severity (Mild, Moderate, and Severe), relationship to study device and procedures (Unrelated, Possibly Related, Definitively Related), TEAEs leading to discontinuation of study participation.
- Any serious adverse events (SAEs), including severity (Mild, Moderate, and Severe), relationship to study device and procedures (Unrelated, Possibly Related, Definitively Related), SAEs leading to discontinuation of study participation
- Any ADEs, including severity (Mild, Moderate, and Severe), relationship to study procedures (Unrelated, Possibly Related, Definitively Related), ADEs leading to discontinuation of study participation
- Any fatal TEAEs, including relationship to study device and procedures (Unrelated, Possibly Related, Definitively Related)

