4.7.2 IDH Events

The number and percentage of subjects will be summarized for the Safety, Evaluable and PP populations, by column size and blood-flow rates combination, for the following:

- Historical IDH Rate (0,1,2,3,4)
- Number of IDH Events (0, 1, 2, 3, 4, 5, 6)
- Change in IDH Rate above the Historical IDH Rate (0, 1, 2, 3)

A listing of IDH Rate, including each subject's historical IDH rate and number of hypotensive events, will be provided.

Protocol Defined IDH Definitions:

Statistical Analysis Plan AKST1210-101

Rev. A Page 16 of 28

Intradialytic hypotension/hypotensive event (IDH)

A systolic blood pressure (SBP) < 90 mmHg that occurs during hemodialysis and is confirmed by repeat measurement.

Expected IDH Rate

The expected number of occurrences of IDH per weekly treatment period derived from a subject's Historical IDH rate (see section below and Protocol Appendix 17.1). The expected IDH Rate is compared

with the actual IDH rate and used to assess escalation, de-escalation, and discontinuation.

Historical IDH Rate

The number of occurrences of IDH as documented in a subject's medical record during a recent 8-week period prior to the run-in period. Subjects with 7 or more IDH events during this 8-week interval will be excluded.

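### SAP 4.1 stops analysing subjects at de-escalation although they stay on the column to V22, so later IDH counts, Hgb values and tolerability outcomes leave the primary summaries; minor: vital-sign baseline is set after column HD starts

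*SAP*

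**What the plan says.** **De-escalation.** SAP 4.1 describes the group as "Subjects who de-escalate (i.e., do not proceed to the next column size and blood-flow rate combination") and states that they "will only be included in analysis up to the point of de-escalation". It names no endpoint and exempts none.

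The protocol describes something different. Under 17.1.2, de-escalation applies at V11 through V19. The subject moves to the previous column size at up to 450 mL/min: S-15 if this happens at V11–V16, S-25 if at V17–V19. "Subjects will continue with the same visit schedule after de-escalation", and the subject "will continue with this column size/flow rate combination through EOT (V22"). Section 17.1.3 plans a further outcome for this group, namely discontinuation where "Subject has already de-escalated and they experience the number of IDH events described in the Table 3" or where Hgb is below 9 g/dL despite optimized ESA treatment.

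The SAP's endpoint sections do not repeat the cut:
- 4.7 presents primary endpoints by combination "and total using both Safety and Evaluable populations".
- 4.7.1: "A TEAE is defined as an AE that occurs on or after the date of the first column use", and all TEAEs are to be reported.
- 4.7.2 tabulates subjects by "Number of IDH Events (0, 1, 2, 3, 4, 5, 6").
- 4.7.3 (Hgb) and 4.7.4 (tolerability) each name a total. The 4.7.4 rows include completion of all visits, and discontinuation for safety, tolerability or investigator discretion.
- 4.3 accounts for every consented subject, with the reason for any discontinuation.

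**Baseline.** SAP 4.1 takes baseline as the first value after HD with the column has begun. The exceptions are labs (last value before column HD) and assessments not made in the treatment weeks (screening). Vital signs fall under neither, and SAP 4.9.3 gives no baseline of its own.

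**The concern.** The SAP treats de-escalation as the end of useful exposure, whereas the protocol treats it as a change of column with follow-up continuing. IDH number, Hgb change and tolerability are all parts of the primary endpoint. The sessions removed belong to subjects who had IDH, anemia or another safety problem, so the loss is not at random. Every removed session is also run at up to 450 mL/min, the condition that the primary objective concerns.

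Three summaries would be incomplete: repeat IDH events on the smaller column (4.7.2), later Hgb values (4.7.3 Total), and the eventual completion or discontinuation of these subjects (4.7.4 Total). Because 4.1 and 4.7.1 conflict and no text says which governs, a programmer would have to decide after seeing open-label data.

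The baseline rule is a smaller matter of the same kind. Any BP change between the V5 pre-HD reading and the first on-column reading is absorbed into baseline, and so is absent from the change-from-baseline BP tables and figures.

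**Working it through.** **The plan's own figure.** Protocol 10.5 and SAP 3.3 give about 70% probability of at least one IDH event per week with 12 subjects at a 10% rate. 1 − 0.9^12 = 71.8%, so it reproduces. It concerns the planned combinations and does not change here.

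**Sessions removed.** Column sessions run from V5 to V22, which is 18. Taking the de-escalation visit *d* as the last one included, sessions lost = 22 − *d*. High-flow sessions are counted as those planned and completed before *d* plus those after it.

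| De-escalation at | Lost | Share of 18 | Share of the subject's high-flow sessions |
|---|---|---|---|
| V11 | 11 | 61% | 11 of 3 + 11 = 14 (79%) |
| V12 | 10 | 56% | 10 of 3 + 10 = 13 (77%) |
| V13 | 9 | 50% | 9 of 3 + 9 = 12 (75%) |
| V18 | 4 | 22% | 4 of 6 + 4 = 10 (40%) |
| V19 | 3 | 17% | 3 of 6 + 3 = 9 (33%) |

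**Which rows can arise from which trigger.**
- IDH: the de-escalation thresholds shown in Protocol Table 3 are more than 1 and more than 2 events in the week. Assuming at most one event per session, the second event comes no earlier than V12 (10 lost) and the third no earlier than V13 (9 lost).
- Hgb: the first scheduled draw inside V11–V19 is at V18 (Protocol 15.3), so a scheduled draw leads to 4 or 3 lost.
- The V11 row needs another reason, or an unscheduled Hgb test.

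**Chance that the removed sessions hold an IDH event (illustration).** The documents give no rate for a subject who has already de-escalated, and no unit for the 10%. At 10% per session with independence, 1 − 0.9^3 = 27% to 1 − 0.9^11 = 69%. At 10% per subject-week, 1 − 0.9^(3/3) = 10% to 1 − 0.9^(11/3) = 32%.

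**Hgb draws.** Protocol 15.3 schedules on-column total and free Hgb at V6, V9, V18 and V21, with total Hgb also at V23. Protocol Table 4, for de-escalated subjects, shows no laboratory tests at V21, although its note says that only column size and flow rate differ from Section 15.
- De-escalation at V11–V17: V18 is lost. That is 1 of 3 on-column draws (33%) if Table 4 holds, or 2 of 4 (50%) with V21 if 15.3 holds.
- De-escalation at V18–V19: 0 of 3, or 1 of 4 (25%), respectively.
- The V23 total Hgb is lost in every case.

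**Tolerability Total (illustration, assumed numbers).** Of 12 subjects, 10 complete without de-escalating and 2 de-escalate. Of those 2, one finishes all visits and one is later discontinued for IDH. Over full follow-up, 11 completed and 1 was discontinued. Under a literal 4.1, the 4.7.4 Total shows 10 and 0.

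**Pooling.** If later sessions were simply added to the planned columns, one subject would contribute 3 + 3 = 6 (S-25, after V19) to 3 + 11 = 14 (S-15, after V11) sessions to a combination planned for 3.

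**Vital signs.** Protocol 7.1.1.2.2 records BP before HD, about every 30 minutes during it, and at the end; other vital signs are taken at the beginning and end of the visit. The first value after column HD starts is therefore the BP about 30 minutes into V5, and the end-of-V5 value for heart rate, respiratory rate and temperature. A pre-HD V5 value is collected for all of them.

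**The case against.** **The events are not hidden.** All IDH after consent is recorded as an AE, listings carry all data with the combination shown, 4.3 keeps every discontinuation with its reason, and 4.7.1, as the more specific section, can be read to override 4.1. This stands in large part. A reader might infer that later IDH events survive only in listings, or vanish; the documents do not support that. But 4.7.1.1 counts a subject once per preferred term, so the TEAE tables cannot replace 4.7.2, the only summary of the number of IDH events per subject.

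**A cut keeps combinations comparable.** This also stands. The planned 3-session columns are right to exclude later sessions, and 4.7.2 takes its total only from the general sentence in 4.7. Likewise, V18 and V21 are planned S-35 visits, so S-15 or S-25 values need to be kept apart there. That argues for a separate column, not for dropping the data from Total.

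**4.7.4 and 4.3 need not match anyway.** Correct. Section 4.3 covers all consented subjects and all reasons, while 4.7.4 covers the analysis populations and three kinds of reason. A reader might infer that any difference between the two is an error caused by 4.1; it is not. The valid complaint is narrower: for the same subjects and the same reasons, the two should be consistent.

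**A pre-HD vital-sign baseline has its own mismatch.** It does. A reader might note that half of the later heart rate, respiratory rate and temperature values are pre-HD values set against an end-of-session baseline, and take that as grounds for the change. A pre-HD baseline produces the mirror image for the other half, and it mixes column effects with those of ordinary dialysis. The case rests only on wanting a pre-column reference.

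**Scale.** The study is small and descriptive, and departures from the SAP are to be noted in the CSR. That limits the consequence but does not resolve the contradiction.

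**Conclusion.** The main point holds. SAP 4.1 ends analysis where Protocol 17.1.2 and 17.1.3 still plan column exposure and an outcome. Literal use removes 3 to 11 of 18 column sessions per de-escalated subject, all at up to 450 mL/min: 3 to 10 for an IDH trigger (assuming at most one event per session), and 3 or 4 for a scheduled Hgb trigger. The 61% figure is an outer limit, not a typical case.

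What is lost is the later part of the 4.7.2 counts, of the 4.7.3 Total, and of the 4.7.4 completions and safety, tolerability or investigator-discretion discontinuations. The planned by-combination columns and the events that trigger de-escalation are unaffected. Loss of the V21 Hgb draw cannot be asserted until Protocol 15.3 and Table 4 are reconciled. No study-wide size follows, because the documents give no expected number of de-escalations; with none, the effect is nil.

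The vital-sign baseline is a real but minor point. The size of any BP offset is not given. Observed values, IDH counts, Hgb, other labs, b2M and ECG are untouched, and the offset cancels in within-subject contrasts between combinations.

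**What to change.** 1. **Limit the cut.** State in SAP 4.1 that it applies only to the planned by-combination columns, and describe de-escalation as Protocol 17.1.2 does.
2. **Keep the later data.** State that TEAE, IDH, Hgb and tolerability summaries include all on-study post-baseline data through EOS, with baseline values kept as defined. Apply the same rule to the Safety population and to any Evaluable and PP versions.
3. **Show it separately.** Put post-de-escalation sessions in a flagged column by the column size and flow rate actually used, with sessions as the denominator, and include them in Total.
4. **Tolerability Total.** Count completions and safety, tolerability or investigator-discretion discontinuations over full follow-up, consistent with 4.3 for the same subjects and reasons. Full agreement with 4.3 is not required.
5. **Hgb schedule.** Reconcile Protocol 15.3 with Table 4 on laboratory tests at V21.
6. **Vital signs (minor).** Use the last value before the first column HD (V5 pre-HD), as is done for labs, and present pre-HD, intradialytic and post-HD changes separately.

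The analysis changes need SAP wording, one extra flagged column in the affected tables, one changed baseline flag, and the split of the vital-sign tables by timing. They need no new data. Item 5 is a protocol clarification.

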4.2 Study Populations for Analysis

4.2.1 Safety Population

The Safety population will consist of all subjects who received at least 1 (or partial) HD treatment with the column.

4.2.2 Evaluable Population

The Evaluable population will consist of all subjects who completed blood-flow rates up to 450 mL/min for at least 1 column size (e.g., S-15 at 250 and up to 450 mL/min).

4.2.3 b2M Population

The b2M Population will consist of a subset of the evaluable population that excludes any subjects with Major Protocol Deviations pertaining to blood flow rate as well as any subjects who have documented blood flow rate deviations exceeding +/- 20 mL/min of the protocol-specified blood flow rate at Visits 4, 7, 10, 13, 16, 19 and/or 22.

4.2.4 Per-Protocol Population

The Per-Protocol (PP) population will consist of all subjects who completed the study without any Protocol Deviations that impact analyses.

